The Surgical Apgar Score (SAS) is a simple 10-point score involving intraoperative variables of estimated blood loss, blood pressure, and heart rate for composite mortality and morbidity. The SAS has varying predictive accuracy across surgical specialties (8,9) and its addition has not significantly improved preoperative risk prediction (10). Since the initial publication of the SAS in 2007 (11), there has been increasing interest in elucidating the role of intraoperative hemodynamics on mortality and morbidity, including hypotension (12,13), heart rate (14,15), anesthetic depth (16), end-tidal carbon dioxide (17) and oxygen saturation (18). A recent systematic review on hypotension found that due to heterogeneity and methodological limitations, one cannot conclude based on available evidence that intraoperative hypotension causes adverse outcomes (12). The impact of blood pressure perioperatively is physiologically complex, with factors including autoregulation, microvascular dysfunction, and limitations of measurement (19).

Our understanding of the impact of intraoperative hemodynamics remains limited as they have been mostly evaluated in isolation. The interactions between intraoperative hemodynamic variables have not been systematically evaluated for association with postoperative outcomes. Hemodynamics are a reflection of physiology, surgical stress, and medications. If found to be predictive of outcomes, automatically recorded hemodynamic variables could provide robust, objective risk stratification within intraoperative anesthesia information systems.

We would like to leverage machine learning to elucidate hemodynamic contributors in the perioperative surgical, physiologic and pharmacologic milieu in the non-cardiac surgery population. Machine learning refers to a set of advanced statistical techniques to evaluate the correlations and associations within large data sets (20). This includes logistic regression with

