The results of this study may help synthesize complex intraoperative clinical information and unveil novel therapeutic strategies. Derived from data from the QEII Hospitals, the results would be directly applicable to the care of Nova Scotians. The models may lead to the creation of objective risk stratification scores calculated at the end of surgery, to identify high risk patients for increased postoperative follow-up and monitoring. Moreover, if models created using machine learning perform well, machine learning may be used more frequently to reveal the patterns within complex, large perioperative datasets. Hemodynamics are potentially modifiable risk factors. Future research includes prospective studies on whether targeted hemodynamic goals, increased postoperative follow-up of high-risk patients, and real-time machine learning precision medicine could improve outcomes after surgeries.

Specific aims

1. To use machine learning techniques to investigate systematically intraoperative hemodynamic predictors of postoperative 30-day all-cause mortality (primary outcome) and major in-hospital morbidity. Hemodynamic predictors to be studied are blood pressure, heart rate, oxygen saturation, end-tidal carbon dioxide, and medications to adjust blood pressure. Please see “Outcomes” section below for full list of secondary outcomes.
2. To evaluate performance of machine learning models created and compare the performance of the best model to the Surgical Apgar Score.

Hypothesis

Controlling for other predictors, the durations of mean arterial pressure (MAP) <65mmHg, heart rate <60 or >100 beats per minute (BPM), hemodynamic medications use, oxygen saturation (SpO₂) <88%, and end-tidal carbon dioxide (EtCO₂) <30 or >45 will be associated with postoperative 30-day all-cause mortality (primary hypothesis) and 30-day major in-hospital morbidity (secondary hypothesis). Note that blood pressure, heart rate, vasopressors and

inotropic medications, oxygen saturation, and end-tidal are considered key indicators of hemodynamics. We have chosen conventional ranges commonly used in practice, and will perform sensitivity analysis of different definitions of each hemodynamic variable.

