In addition, the model for hemodynamic predictors of postoperative mortality developed from machine learning will perform better in terms of discrimination (C-statistics), calibration (Hosmer-Lemeshow test), and risk reclassification (Yates slope and integrated discrimination improvement) than the Surgical Apgar Score.

Methodology

Study Design Overview

This is a retrospective population cohort study. Following approval from the Research Ethics Board, we will analyze de-identified records of our study population. Since there are many machine modelling techniques each with its benefits and drawbacks, we will create models using interpretable machine learning techniques we believe will work the best for this study, and test the performances of these models through internal validation. The models will be compared to the Surgical Apgar Score in terms of discrimination, calibration, and risk reclassification. The trial will be registered on ClinicalTrials.gov prior to receiving research data and performing analysis. Transparent reporting of a multivariable prediction model for individual prognosis or diagnosis (TRIPOD) and Developing and Reporting Machine Learning Predictive Models (24) guidelines will be followed.

Study Population

We will include all patients ages ≥ 45 receiving their index (i.e. first) non-cardiac surgery with an overnight stay at the Nova Scotia Health Authority Queen Elizabeth II (QEII) hospitals (Victoria General and Halifax Infirmary) Halifax, Canada, from the past five years (i.e. January 1, 2013 to December 1, 2017). For patients who had multiple surgeries, only the first non-cardiac surgery with an overnight stay at QEII will be included to avoid confounding from previous surgical admissions (i.e. one surgical admission per patient). We chose December 1, 2017, as the end date to allow for complete data 30 days after surgery: for data analysis in summer 2019, we only have access to mortality data up to December 31, 2017.

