 5. Delirium
 6. Septic Shock
2. Postoperative ICU admission (yes/no)
3. Prolonged Postoperative Length of Stay (LOS) (greater than vs. less than or equal to CIHI Expected Length of Stay (ELOS) as assigned by the Case Mix Grouping) [note that the LOS includes the day of surgery]
4. Hospital readmission within 30 days (yes/no)
5. Intraoperative mortality (yes/no)
6. Days alive and out of hospital at 30 days postoperatively (28)

III. Other predictors included into model

The following potential perioperative predictors will be evaluated as covariates during model building. Statistically significant predictors will be retained in the model.

Table 2. Other predictors

Preoperative	
 1. Demographics: age on date of surgery, sex, obesity (body mass index>30) 2. Indicators of preoperative comorbidities: since no comorbidity score has perfect performance, a variety of models will be evaluated and the most significant predictive score will be retained in the model. 
 • American Society of Anesthesiologist class • RCRI score(29), and specific components via ICD codes (history of ischemic heart disease, congestive heart failure, cerebrovascular disease, diabetes, chronic kidney disease, and CCI and Case Mix Group codes of suprainguinal vascular, intraperitoneal, or intrathoracic surgery) using previously published methods (30)(31) • Elixhauser comorbidity index (32) and Charlson Comorbidity Index (33): calculated using diagnoses from the previous three years according to standard algorithm by HDNS. Reported as both total score and individual categories • Hospital Frailty Risk Score (34): based on ICD codes • Preoperative blood pressure: ICD diagnosis of hypertension and by measured blood pressure • Preoperative heart rate: Innovian and HSM • Chronic Obstructive Lung Disease (ICD code): since it may affect the interpretation of results of SpO₂ and EtCO₂ 3. Indicators of surgical complexity 
 • CIHI DAD Case Mix Group (CMG) class (also contains categories that include medical complexity) • Main Surgical Service • Procedural Index for Mortality Risk (PIMR) (35): according to CCI • Procedure: CCI codes • Preoperative ICU admission • Emergency surgery: as determined by DAD Method of Entry = emergency department or transferred from another institution)

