The performance of all models created will be evaluated in the validation set as part of internal validation using the same metrics of discrimination, calibration, and risk reclassification, and compared to the Surgical Apgar Score. Since there will likely be significant class imbalance and ROC curves may overestimate model performance, for each model, precision and recall curves (PRC), F score, average precision, and AUC will also be reported and compared. The best performing model will also be used to analyze for predictors for secondary outcomes. Sensitivity (recall, true positive rate), specificity, positive predictive value (precision), G-mean, negative predictive values, False Discovery Rates (FDR), optimism, and measures of association of hemodynamic thresholds for primary and secondary outcomes will be computed. Bayesian network causal inference analysis may be performed, to help increase interpretability.

Sensitivity and subgroup analysis

Sensitivity analysis will be performed for different definitions of hemodynamic derangements. Subgroup analysis will be performed based on age, sex, high preoperative risk (most significant indicator of preoperative comorbidity in Table 2, based on final model), RCRI, frailty (HFRS), preoperative hypertension, a select list of intermediate-high risk, gender-neutral elective surgery (please see Appendix – RCRI Protocol Table 1), emergency surgery, and type of anesthesia.

Power calculation

The 2016-2017 in-hospital mortality after major surgery in Nova Scotia is 1.7% (47). Using the Events Per Variable criterion (EPV) of at least 10 outcomes per predictor in the sample, the 1.7% mortality (408) out of an estimated sample size of 24,000 for the derivation/training group means that our model would be valid for up to 41 predictors for the primary outcome. However, the EPV may over or underestimate the limitations of the EPV criterion (48), square root of the mean squared prediction error (rMPSE) and mean absolute prediction error (MAPE) will be calculated based on the number of predictors, sample size and events fraction (49) with the caveat that this model has not been externally validated. Full power calculation will be performed once we receive the final sample size.

Strengths

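### Beating the Surgical Apgar Score cannot show that the hemodynamic variables add predictive performance; a covariates-only comparator is missing

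*Combined protocol and SAP*

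**What the plan says.** Aim 2 (Specific aims) is to evaluate the machine learning models and "compare the performance of the best model to the Surgical Apgar Score". The Hypothesis section turns this into a prediction: "the model for hemodynamic predictors of postoperative mortality developed from machine learning will perform better in terms of discrimination", calibration and risk reclassification than that score. Under Evaluating model performance, all models are assessed in the validation set "using the same metrics of discrimination, calibration, and risk reclassification, and compared to the Surgical Apgar Score". No other reference model is named, and none is named for the integrated discrimination improvement (IDI).

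The two sides hold different information. On the comparator, Background and significance says: "The Surgical Apgar Score (SAS) is a simple 10-point score involving intraoperative variables of estimated blood loss, blood pressure, and heart rate". Appendix 1 gives its items as estimated blood loss, lowest MAP and lowest heart rate. The machine learning models start from the Table 1 hemodynamic exposures and add Table 2: "The following potential perioperative predictors will be evaluated as covariates during model building", followed by "Statistically significant predictors will be retained in the model". Table 2 covers demographics, ASA class, RCRI, Elixhauser, Charlson, the Hospital Frailty Risk Score, Case Mix Group, the procedural mortality index, procedure codes, emergency status, anesthetic factors and bleeding measures.

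Separately, the primary hypothesis is an adjusted association: "Controlling for other predictors, the durations of mean arterial pressure (MAP) <65mmHg" and the other listed exposures are expected to be associated with 30-day mortality. The plan also says that "measures of association of hemodynamic thresholds for primary and secondary outcomes will be computed".

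**The concern.** The comparison changes two things at once: the detail of the hemodynamic data, and the presence of all preoperative and surgical risk information. The comparator is not free of hemodynamics either, since two of its three items are MAP and heart rate. A margin over it therefore cannot be assigned to the Table 1 variables, although the Hypothesis section labels the expected winner as the model for hemodynamic predictors.

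The plan's rationale depends on that assignment. Background and significance faults preoperative scores for leaving out intraoperative hemodynamics, and reports that adding the Surgical Apgar Score to preoperative prediction has not helped significantly. It then looks ahead to risk scores calculated at the end of surgery, and Future directions to real-time tools. Each rests on whether intraoperative hemodynamics improve prediction over what is otherwise known about the patient and operation. If a win over the Surgical Apgar Score were reported as evidence of that, the claim would be unsupported.

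**Working it through.** **1. The plan's own figure.** Power calculation: 0.017 × 24,000 = 408 deaths, and 408 / 10 = 40.8, stated as 41 predictors. It reproduces. It is the only sizing figure; none is given for the Surgical Apgar (SAS) comparison, and no expected C-statistic is stated.

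**2. What the planned contrast contains.** By identity,

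C(full) − C(SAS) = [C(full) − C(covariates)] + [C(covariates) − C(SAS)].

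Only the first bracket is added value over the covariates. The second can be large with no hemodynamic contribution. The plan estimates the sum and neither bracket.

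**3. Illustration; every effect size and correlation is an assumption.** Logistic model with a 1.7% event rate and three standardised scores: X (covariates), S (an SAS-type score) and H (hemodynamic durations). S has correlation 0.3 with X. H = 0.3X + 0.4S + noise, so its correlation with X is 0.3 + 0.4 × 0.3 = 0.42, and with S it is 0.4 + 0.3 × 0.3 = 0.49. The log odds ratio per SD of X is 0.8, 1.2 or 1.6. Models with S only, X only, and X + S + H were fitted on 200,000 patients and scored on another 200,000. Each cell gives C(full) − C(SAS), then C(full) − C(covariates).

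| Log odds ratio for S, H | X = 0.8 | X = 1.2 | X = 1.6 |
|---|---|---|---|
| 0, 0 | 0.136; 0.000 | 0.194; 0.000 | 0.234; 0.000 |
| 0.3, 0 | 0.094; 0.010 | 0.149; 0.007 | 0.182; 0.004 |
| 0.3, 0.3 | 0.098; 0.023 | 0.138; 0.014 | 0.176; 0.007 |
| 0.3, 0.6 | 0.107; 0.039 | 0.144; 0.026 | 0.168; 0.015 |

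Worked cell (0.3, 0.3; X = 1.2): C is 0.705 for SAS, 0.829 for covariates and 0.843 for full. The gap is 0.843 − 0.705 = 0.138, of which 0.843 − 0.829 = 0.014 is added value and 0.829 − 0.705 = 0.124 is covariates.

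In the top row, where S and H have no effect given X, the IDI against SAS is still 0.014, 0.039 and 0.083. Against covariates alone it is 0.000. In each column the gap over SAS is larger with no effect than with one, so its size does not track hemodynamic value. The nested difference separates the null row from the others.

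**4. At the study's scale.** The documents allow several validation sizes. If 24,000 is 80% of the cohort, the total is 24,000 / 0.8 = 30,000 and validation has 6,000 (102 deaths at 1.7%). If the cohort is 35,000, validation has 35,000 − 24,000 = 11,000 (187 deaths). An 80:20 split of 35,000 gives 7,000 (119 deaths), in between. With X = 1.2, 24,000 training patients and 150 replicates per setting:

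- No effect of S or H: the full model beat SAS in every replicate. The mean gap was 0.197 (SD 0.034) at 6,000 and 0.200 (SD 0.025) at 11,000. The nested difference averaged −0.0004 (SD 0.0015) and −0.0003 (SD 0.0013).
- S and H both 0.3: the nested difference averaged 0.0135 (SD 0.0079) and 0.0126 (SD 0.0056), about 0.0135 / 0.0079 = 1.7 and 0.0126 / 0.0056 = 2.25 SDs from zero.

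**The case against.** The strongest reply is that the comparison answers its own question. Aim 2 is a benchmark against an existing score calculated at the end of surgery, which is the intended use of the new model. The Hypothesis section predicts better performance without saying that the margin comes from Table 1; the wording about hemodynamic predictors may be only a label. This stands, and the benchmark should be kept.

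A reader might go further and infer that the plan cannot address hemodynamics at all. The documents do not support that. The primary hypothesis is an adjusted association, association measures for hemodynamic thresholds are planned, and variable selection and random forest importance (Creating the models) bear on which exposures matter. None of these measures the gain in held-out prediction, and that gap is the whole of this point.

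A reader might also infer that the performance hypothesis is bound to be confirmed. That is too strong: it also covers calibration, where a richer model need not win. The argument holds for discrimination and IDI. Nor should the imbalance be put as a count of candidate covariates against three items. Only significant predictors are retained, and the stated sizing is for up to 41.

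Finally, Background and significance does not set added value over preoperative information as the single open question. It mentions that contrast as one cited study's result, and elsewhere stresses that hemodynamic variables have been studied in isolation.

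**Conclusion.** The point holds in this limited form. The plan has no test of incremental predictive performance for the Table 1 variables, and superiority over the Surgical Apgar Score cannot stand in for one. This follows from the contents of the two models and needs no numerical assumption.

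The sizes do rest on assumptions. In the range tried, a model with no hemodynamic contribution leads the score by 0.14 to 0.23 in C-statistic. When S and H both have effects the lead is 0.10 to 0.18, with a gain over covariates of 0.007 to 0.039. These figures show the mechanism and are not forecasts for this cohort.

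The primary hypothesis is untouched. The point bears on how aim 2 is interpreted, and is worth fixing because the change is cheap and can be prespecified.

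**What to change.** Prespecify, with the same learner, derivation/validation split, tuning and class rebalancing:

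- **(a)** a covariates-only model from an explicitly defined Table 2 block;
- **(c)** the same block plus the Table 1 exposures;
- optionally **(b)**, the block without separate blood loss plus the Surgical Apgar Score, so that blood loss is not entered twice.

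The block needs care. Table 2 mixes preoperative variables with intraoperative and postoperative ones: blood loss, transfusion, lowest hemoglobin within two days after surgery, and the anesthetic factors. List these separately and say which enter (a), so that it is clear whether the reference is preoperative information or everything except Table 1. Temperature also needs assigning: Table 2 treats it as a covariate and Appendix 1 calls it an exposure.

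Report (c) minus (a) in C-statistic, Brier score and IDI, with paired bootstrap confidence intervals in the validation set. Base any statement about hemodynamic added value on that contrast. Keep the Surgical Apgar comparison as a benchmark. The plan does not say how the 0 to 10 score becomes a probability, which calibration, Brier score and IDI require; fit it by logistic regression in the derivation set.

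The cost is one or two extra fits on data already held, plus some wording. The drawback is that the nested gain will probably be much smaller than the gap over the Surgical Apgar Score. With roughly 100 to 190 validation deaths, its interval may include zero even if a modest effect exists.

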Several techniques exist to make the learning algorithms to focus on the important class (44). Among these, pre-processing techniques are a powerful tool enabling the use of any standard learning algorithm by modifying the training set. The goal is to obtain a more balanced training set through weighting, undersampling and/or oversampling. We will explore different resampling techniques to rebalance the training set. Regarding undersampling, we will explore both random and informed undersampling (remove examples near the decision border through nearest neighbours computation and use a clustering algorithm to guide the selection of examples). For oversampling, we will explore the introduction of replicas (randomly or by weighting) and the generation of synthetic data through the introduction of Gaussian Noise, SMOTE, and other SMOTE-based techniques. We will also examine the combination of these techniques. All of these techniques are only applied on the training set used to learn the model, and they are never applied on the test set. Thus, the model, although learned in a more balanced scenario is always evaluated only in real data and in a real imbalanced scenario.

We will also apply cost-sensitive learning. The assignment of higher costs to type II errors during learning has the potential to improve the results, reducing this type of error. The effect of class rebalancing (at a variety of ratios and through a variety of techniques) on model performance will be examined, and the impact of these adjustments on model performance will be reported.

Evaluating model performance

Using the derivation/testing set, the performances of machine learning models generated will be evaluated by cross validation. To account for potential temporal effects and concept drift, Monte Carlo and prequential evaluation will be used (45). In addition, each model will be evaluated in terms of discrimination, calibration, and risk reclassification (21,46). Discrimination will be calculated through C-statistics using area under curve (AUC) of receiver operating characteristic curve (ROC). Calibration will be represented graphically using observed vs.

expected event rates in risk estimate deciles, and by the Hosmer-Lemeshow statistic. Brier score will be computed for discrimination and calibration. Risk reclassification will be quantified through Yates slope and integrated discrimination improvement. R-squared will be reported.

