Innovian	Surgical APGAR Score [Derived by Innovian based on variables already requested]	Patient	Jan 1, 2013 to Dec 1, 2017	
  
 	0 points	1 point	2 points	3 points	
   
 Estimated blood loss (mL)	> 1,000	601–1,000	101–600	≤ 100	
 
 Lowest mean arterial pressure (mmHg)	< 40	40–54	55–69	≥ 70	
 
 Lowest heart rate (beats/min)	> 85	76–85	66–75	56–65	
 
 Surgical score (0-10) = sum of all points	
 
 The Surgical APGAR Score is an existing, validated method of risk stratification at the end of surgery, and will be compared to the machine learning models.	
  
		0 points	1 point	2 points	3 points	Estimated blood loss (mL)	> 1,000	601–1,000	101–600	≤ 100	Lowest mean arterial pressure (mmHg)	< 40	40–54	55–69	≥ 70	Lowest heart rate (beats/min)	> 85	76–85	66–75	56–65	Surgical score (0-10) = sum of all points					The Surgical APGAR Score is an existing, validated method of risk stratification at the end of surgery, and will be compared to the machine learning models.					4 points
	0 points	1 point	2 points	3 points																															
Estimated blood loss (mL)	> 1,000	601–1,000	101–600	≤ 100																															
Lowest mean arterial pressure (mmHg)	< 40	40–54	55–69	≥ 70																															
Lowest heart rate (beats/min)	> 85	76–85	66–75	56–65																															
Surgical score (0-10) = sum of all points																																			
The Surgical APGAR Score is an existing, validated method of risk stratification at the end of surgery, and will be compared to the machine learning models.																																			
Mortality																																			
Vital Statistics	Mortality (30-day all cause) [Derived by HDNS based on DOD from Vital Statistics]	Patient	Jan 1, 2013 to Dec 31, 2017	Binary outcome (yes/no), derived from DOD within 30 days from PDATE. This is needed to compute 30-day all-cause mortality. Primary outcome for the study to be used for modeling.																															

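### The plan claims better calibration than the Surgical Apgar Score, but names a single-model fit test, gives no between-model calibration measure, and does not convert the score to a predicted risk

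*Combined protocol and SAP*

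**What the plan says.** - **Hypothesis.** The model developed by machine learning "will perform better in terms of discrimination (C-statistics), calibration (Hosmer-Lemeshow test), and risk reclassification" than the Surgical Apgar Score. The Hosmer-Lemeshow test is the only calibration measure named there. The comparison with the score is the second of the two Specific aims.
- **Evaluating model performance.** Calibration is to be shown graphically as observed against "expected event rates in risk estimate deciles, and by the Hosmer-Lemeshow statistic". In addition, "Brier score will be computed for discrimination and calibration".
- **Same section, validation set.** All models are evaluated "using the same metrics of discrimination, calibration, and risk reclassification, and compared to the Surgical Apgar Score". No calibration intercept or slope is listed. No between-model difference with an interval is given, and no rule says what counts as better.
- **Appendix 1, Surgical APGAR Score.** The comparator is defined by points: "Surgical score (0-10) = sum of all points". No conversion to a probability of death is described.
- **Class Imbalance.** The training set is to be rebalanced by weighting, undersampling, oversampling and synthetic data, and cost-sensitive learning is also planned. Evaluation stays on unaltered data. No recalibration step is described.

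**The concern.** Calibration is one of three parts of the claimed advantage over the Surgical Apgar Score. Hosmer-Lemeshow has a null hypothesis about one model's fit and none about two models. A larger p-value for one of them does not mean that it is better calibrated. The statistic grows with sample size for a fixed fault, changes with the grouping, and does not show whether risks are too high or too low.

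The comparison is also undefined on the comparator's side. Calibration compares predicted probabilities with observed frequencies, and a points total is not a probability. Once a mapping exists, the score's natural groups are its levels, so the number of groups and the degrees of freedom would differ from the model's ten.

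The question matters in practice because rebalancing moves predicted risks away from the true event rate. Miscalibration of the model is therefore foreseeable, and the plan needs a measure that shows how large it is and in which direction.

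**Working it through.** **The plan's own figure.** Power calculation gives "the 1.7% mortality (408) out of an estimated sample size of 24,000 for the derivation/training group", with "at least 10 outcomes per predictor in the sample". 24,000 × 0.017 = 408, and 408 / 10 = 40.8, stated as 41. This reproduces.

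**Validation size (not stated).** Study Population gives about 35,000 patients, Creating the models gives a split of roughly 80:20, and Power calculation gives 24,000 for derivation. These allow three readings:
- 24,000 is 80%: 24,000 / 0.8 × 0.2 = 6,000, with 6,000 × 0.017 = 102 deaths
- 20% of 35,000: 7,000, with 119 deaths
- 35,000 − 24,000: 11,000, with 187 deaths

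**Does the test pick up a known fault?** Assumptions: linear predictor normal with SD 0.75, 1.5 or 2.0, which gives C-statistics of 0.70, 0.85 and 0.905 at 1.7% deaths; ten equal groups; 10 df, because the model is not fitted in the validation data; 5% level. None of these is stated in the plan. The fault is every predicted risk multiplied by 1.3. Rejection rates from 2,000 simulated sets per cell:

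| C-statistic | n = 6,000 | n = 7,000 | n = 11,000 |
|---|---|---|---|
| 0.70 | 25% | 32% | 64% |
| 0.85 | 28% | 36% | 68% |
| 0.905 | 28% | 38% | 67% |

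At C of about 0.85-0.90, independent repeats gave 23-30%, 33-39% and 62-70%. The fault is identical in every column, and only the sample size changes.

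**What a direct measure shows for the same fault.** Observed / expected deaths = 1 / 1.3 = 0.77. The standard error of its logarithm is about 1/√(deaths) (Poisson approximation).
- n = 6,000: 1/√102 = 0.099, so the 95% interval is 0.77 × exp(±1.96 × 0.099) = 0.63 to 0.93
- n = 7,000: 1/√119 = 0.092, interval 0.64 to 0.92
- n = 11,000: 1/√187 = 0.073, interval 0.67 to 0.89

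At the expected number of deaths, calibration-in-the-large states the direction and the size at all three validation sizes.

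**Does comparing two results carry information?** In 600 simulated sets of 7,000, a continuous model and a coarse score on the 0-10 scale were both perfectly calibrated. The continuous model had the larger Hosmer-Lemeshow p-value in 53% of sets, and the two results disagreed at 0.05 in 9.5%. Neither was better calibrated, so any ranking was noise.

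**Grouping of the score.** Three assumed unimodal distributions of the 0-10 score, cut at their tenths, gave 6 or 7 unequal groups against ten equal ones for the model.

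**Rebalancing.** If training were balanced 1:1 (one possible ratio; the plan will explore several), the odds would be inflated by about 0.983 / 0.017 = 57.8, unless predictions were corrected afterwards.

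**The case against.** The strongest reply is that the hypothesis mentions Hosmer-Lemeshow only in a parenthesis, while the operative section lists a plot first, then the statistic, and a Brier score. The plot does show size and direction. That is right, and it rules out the reading that calibration will be judged by this test alone. But the plot gives no between-model quantity or interval, and the Brier score mixes discrimination with calibration, so a sharper model can win on it without being better calibrated.

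Three stronger readings are tempting, and the documents do not support them:

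- *That the plan lets a bad model pass and a good one fail.* No significance level, threshold or comparison of p-values is stated. The gap is the missing measure and rule, not a faulty rule.
- *That sparse low-risk deciles invalidate the test.* At n = 7,000 the lowest decile expects 0.3 deaths at C = 0.85 but 2.6 at C = 0.70, yet rejection of the 30% fault is similar (36% and 32%). A perfectly calibrated model is rejected in 6-8% of sets of 7,000 at C of about 0.85-0.90 with 10 df, which is near nominal. The 12-15% seen with 8 df needs a choice that the plan does not make.
- *That the score cannot be grouped at all.* It cannot form ten equal groups, but score levels can serve as groups. The consequence is non-comparable statistics.

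It is also fair that gross miscalibration would be caught: a 1:1 prior shift was rejected in all 500 simulated sets of 7,000. Finally, this comparison is additional to the primary hypothesis, which concerns association with mortality.

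**Conclusion.** The concern holds in a limited form. The plan asserts better calibration than the Surgical Apgar Score, names a test that cannot show it, and offers no between-model calibration measure in its place. The comparator has no predicted risk to calibrate. This part of the conclusion follows from the text and needs no assumption.

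The size is illustrative. With 1.7% deaths, an assumed C-statistic of about 0.85-0.90 and 10 df, a uniform 30% over-prediction is flagged in about 26-30%, 34-39% or 67% of validation sets at 6,000, 7,000 or 11,000 patients. The 1.7% is an in-hospital rate that the plan uses as its planning value for 30-day mortality. The association hypotheses are unaffected. The change should be made before the validation data are analysed.

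**What to change.** 1. In the derivation set, fit a logistic regression of 30-day death on the Surgical Apgar Score, so that the score yields predicted risks.
2. Where training used rebalancing or cost weights, recalibrate the model to the original derivation-set event rate. Then lock both the model and the mapping.
3. In the validation set, report calibration-in-the-large, calibration slope and the mean absolute distance between predicted risk and a smooth calibration curve, for the locked model and for the mapped score. Use the same smoother for both.
4. Give paired bootstrap 95% intervals (resampling patients) for the difference in calibration error. Replace the Hosmer-Lemeshow test in the hypothesis with these measures, and state in advance what will count as better, for example an interval for the difference that lies wholly on the model's side of zero.
5. Keep the decile plot, Brier score and Hosmer-Lemeshow statistic as descriptive, and base no comparative claim on the last.

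The cost is revised wording in two sections and a little more analysis code. No new data or variables are needed.
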